| C_{max} | Maximum serum concentration |
| CRU | Clinical research unit |
| CV | Coefficient of variation |
| DBP | Diastolic blood pressure |
| ECG | Electrocardiogram |
| eCRF | Electronic Case Report Form |
| eGFR | Estimated glomerular filtration rate |
| EMA | European Medicines Agency |
| FDA | Food and Drug Administration |
| GMR | Geometric mean ratio |
| HR | Heart rate |
| ICH | International Conference on Harmonisation |
| IP | Investigational product |

| | |
|-------------|--|
| IPD | Important protocol deviation |
| MedDRA | Medical Dictionary for Regulatory Activities |
| N/A | Not available |
| NAb | Neutralizing antibody |
| NCA | Non-compartmental analysis |
| NCI-CTCAE | National Cancer Institute Common Terminology Criteria for Adverse Events |
| PD | Protocol deviation |
| PK | Pharmacokinetics |
| PT | Preferred term |
| QTcF | QT interval corrected using Fridericia's correction |
| RR | Respiratory rate |
| SAE | Serious adverse event |
| SAP | Statistical analysis plan |
| SBP | Systolic blood pressure |
| SC | Subcutaneous |
| SD | Standard deviation |
| SOC | System organ class |
| $t_{1/2}$ | Elimination half life |
| TEAE | Treatment-emergent adverse event |
| TESAE | Treatment-emergent serious adverse event |
| t_{max} | Time to maximum serum concentration |
| TRAE | Treatment-related adverse event |
| Vd/F | Volume of distribution |
| λ_z | First order rate constant associated with the terminal (log-linear) portion of the curve |

1 INTRODUCTION

This Statistical Analysis Plan (SAP) has been developed based on following study documents:

- Protocol: Version 1.0 (05 Aug 2022)
- Protocol Clarification Letter (05 Sep 2022, 18 Nov 2022, and 27 Jun 2023)
- Electronic Case Report Form (eCRF): Version 2.0 (06 Jan 2023)

This SAP describes the statistical analysis to be conducted for the above mentioned protocol, and has been developed and finalized prior to database lock of the clinical database.

This SAP is being written with consideration of the recommendations outlined in the most recent International Conference on Harmonisation (ICH) E9 Guideline entitled “Guidance for Industry: Statistical Principles for Clinical Trials”, the most recent ICH E9(R1) Guideline entitled “Addendum on Estimands and Sensitivity Analysis in Clinical Trials” and the most recent ICH E3 Guideline entitled “Guidance for Industry: Structure and Content of Clinical Study Reports”.

2 STUDY OBJECTIVES AND ENDPOINTS

| Objectives | Endpoints |
|--|---|
| Primary | |
| Part 1: To evaluate the effect of severe renal impairment on the pharmacokinetics (PK) of HM15912 following single SC dose | 
 • Maximum serum concentration (C_{max}) • Area under the concentration-time curve from extrapolated to infinity ($AUC_{0-\infty}$) |
| Part 2 (if applicable): To evaluate the effect of moderate and mild renal impairment on the pharmacokinetics of HM15912 following single SC dose | |
| Secondary | |
| To evaluate the safety and tolerability of a single SC dose of HM15912 in subjects between mild, moderate and severe renal impairment and normal renal function subjects | 
 • Incidence of adverse events (AEs), treatment emergent AEs (TEAEs) and serious AEs (SAEs) • Changes from baseline in vital signs and 12-lead electrocardiogram (ECG) parameters |
| Exploratory | |
| To assess the immunogenicity of HM15912 after single SC dose in subjects with renal impairment and in subjects with normal renal function | 
 • Anti-drug antibody (ADA) • Neutralizing antibody (NAb) • Anti-polyethylene glycol (anti-PEG) antibody |
| To assess the additional PK parameters of HM15912 in subjects | 
 • Time to maximum serum concentration (t_{max}) • Elimination half-life ($t_{1/2}$) |

| | |
|--|--|
| with renal impairment and in subjects with normal renal function | 
 Volume of distribution (Vd/F) Clearance (CL/F) First order rate constant associated with the terminal (log-linear) portion of the curve (λ_z) Area under the concentration-time curve from time zero to the last observable concentration (AUC_{last}) Percentage of $AUC_{0-\infty}$ due to extrapolation from t_{last} to infinity ($AUC_{\%Extrapol}$) |
|--|--|

3 INVESTIGATIONAL PLAN

3.1 Overall Study Design and Plan

This study is a phase 1, open-label, single-dose, parallel-group study to investigate the effect of renal impairment on the PK of HM15912 in subjects with severe renal impairment and subjects without renal impairment as a control group (Part 1), and in subjects with moderate and mild renal impairment (Part 2).

At Screening, subjects will be enrolled to the appropriate groups based on the classification as defined in the Food and Drug Administration (FDA) draft guidance for industry, "Pharmacokinetics in Patients with Impaired Renal Function – Study Design, Data Analysis, and Impact on Dosing and Labeling" (2020). Subjects with normal renal function and subjects with renal impairment will be classified based on the estimated glomerular filtration rate (eGFR) calculated using the Chronic Kidney Disease Epidemiology Collaboration (CKD-EPI) equation (2021).

Subject screening for participation in this study will be conducted within 28 days prior to investigational product (IP) dosing on Day 1. The mean of the eGFR obtained from two screening visits will be used for group assignment. Second baseline eGFR sample will be taken during the screening period, that are greater than 3 days (72 hours) but no more than 14 days apart from the first eGFR assessment. All subjects must have stable renal function to enter the study which is defined as $\leq 25\%$ difference between 2 measurements of eGFR during the screening period. Subjects will be selected and categorized according to their eGFR as shown in Table 1.

Table 1 Renal Function Categories by eGFR ranges

| Cohort | Renal Impairment | eGFR (mL/min/1.73m ²) | Number of Subjects |
|--------|------------------|-----------------------------------|--------------------|
| 1 | Normal | ≥ 90 | 8 |
| 2 | Severe | < 30 | 8 |
| 3 | Moderate | ≥ 30 to < 60 | 8 |
| 4 | Mild | ≥ 60 to < 90 | 8 |

Approximately 16 subjects will be enrolled in Part 1; 8 subjects with severe renal impairment (Cohort 2) and 8 with normal renal function (Cohort 1). The 8 subjects of Cohort 2 will be recruited first. After the end of recruitment of Cohort 2, the demographics will be pooled to determine an average value for age and weight which will be used as a reference value for Cohort 1. The subjects with normal renal function in Cohort 1 will be recruited later such that each subject's age is within ± 10 years and weight is within ± 15 kg of the mean of the Cohort 2. An attempt will be made to maintain a similar male/female ratio between Cohort 1 and Cohort 2. Care will be taken when recruiting the subjects with normal renal function such that the entire group is not younger and of lower body weight than the impaired subjects.

Part 2 will be conducted if the point estimate of geometric mean ratio (GMR) of $AUC_{0-\infty}$ for the severe renal impairment group (Cohort 2) compared to the control group (Cohort 1) [REDACTED]. Based on whether the decision criterion to proceed to Part 2 is met, up to 8 subjects with moderate renal impairment (Cohort 3) and 8 subjects with mild renal impairment (Cohort 4), matched for demographic character to control group will be enrolled.

For both Parts 1 and 2, subjects who withdraw from the study for non-safety related reasons and who are considered to be non-evaluable with respect to the primary objective may be replaced at the discretion of the sponsor but the maximum number of meaningfully evaluable patients will be not more than planned 8.

Each subject will receive a single dose of either HM15912 administered subcutaneous (SC) in the abdomen on the Day 1, and the assessments will be conducted based on Appendix 13.1 in this SAP. Blood samples will be collected from subjects to determine PK of HM15912 up to 29 days post-dose according to the scheduled pharmacokinetic sampling schedule as below:

Table 2 Pharmacokinetic Sampling Schedule

| Study Day | PK Sampling Time Point | |
|--------------------|------------------------|-----------------------|
| Day 1 | Inpatient Period | Predose |
| Day 2 ^a | | 24 h (± 15 min) |
| Day 3 ^b | | 48 h (± 60 min) |
| Day 4 ^b | | 72 h (± 60 min) |
| Day 5 ^b | | 96 h (± 60 min) |
| Day 6 ^b | | 120 h (± 60 min) |
| Day 7 ^b | | 144 h (± 60 min) |
| Day 8 | | 168 h (± 60 min) |
| Day 10 | Outpatient Period | 216 h (± 24 h) |
| Day 15 | | 336 h (± 24 h) |
| Day 22 | | 504 h (± 24 h) |
| Day 29 | | 672 h (± 24 h) |

a. After completion of study procedures on Day 2, if subjects request to discharge, subjects may be discharged from the Clinical research unit (CRU) on their desired date, at the discretion of investigator If subjects discharge

from CRU, all the remaining procedures will be conducted by outpatient visit.

b. If subjects discharge earlier than Day 8 based on the subject's request, Day 3, 4, 5, 6, and 7 procedures can be done in outpatient visits.

3.2 Treatment Plan

The study drug, HM15912 0.5mg/kg, will be administered once by the authorized site staff via SC injection into abdominal wall.

3.3 Analysis Schedule

After all subjects in Cohort 1 and Cohort 2 have completed all scheduled procedures, preliminary analysis will be conducted to decide whether to proceed to Part 2, or not. Part 2 will be conducted if the point estimate of GMR of $AUC_{0-\infty}$ for the severe renal impairment group (Cohort 2) compared to the control group (Cohort 1) [REDACTED]

If the decision criterion to proceed to Part 2 is met, final analysis will be conducted after all subjects who are enrolled in the Part 2 complete or discontinue the study. However, if the decision criterion to proceed to Part 2 is not met, final analysis will be conducted follow up with preliminary analysis.

4 DETERMINATION OF SAMPLE SIZE

The planned sample size of 8 subjects for each cohort is selected to characterize the effect of renal impairment on the PK of HM15912 based on FDA and European Medicines Agency (EMA) guideline rather than calculated with consideration of statistical requirements. With 8 subjects for each cohort (renal impairment cohort and normal renal function cohort), half width of two-sided 90% confidence interval of natural log scaled $AUC_{0-\infty}$ difference between two cohorts is 0.2260 with consideration of between-subject standard deviation, 0.257, from the previous phase I study result of HM15912. This provides the 90% confidence interval (0.798, 1.254) for a geometric mean ratio of 1.0.

As stated in the study design part, approximately 16 subjects will be enrolled in Part 1 (8 subjects with severe renal impairment and approximately 8 subjects with normal renal function). If Part 2 is conducted, 8 subjects with moderate renal impairment and 8 subjects with mild renal impairment will be enrolled.

5 ANALYSIS SET

An analysis populations classification will be discussed to decide which subjects and/or data will be excluded from certain analyses. The decisions will be made before the database lock and will be documented and approved.

In this study, the following populations are defined.

Table 3 Analysis Set Definition

| Population | Description |
|---------------------|--|
| Screened Population | All subjects who signed the Informed consent form to proceed with screening. This population will be used only for the disposition summary and by-subject listings. |
| Safety Population | All subjects who received any amount of HM15912. All analyses other than that specified will be performed based on safety population. |
| PK Population | All subjects who have at least one evaluable HM15912 serum concentration after receiving any amount of HM15912 without important protocol deviations (IPDs) or events (i.e. significantly affect the PK of study drug). PK parameter analyses will be conducted with PK population. |

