HM15912 has been evaluated in one clinical study to date. A first-in-human study (HM-GLP2-101) was a Phase 1 double-blind, randomized, placebo-controlled, single ascending dose (SAD) study to assess the safety, tolerability, pharmacokinetics and pharmacodynamics of the SC administration of HM15912 in healthy subjects conducted in Korea. The study was conducted in 5 sequential dosing cohorts enrolling 8 subjects per cohort. Subjects were randomized to HM15912 or placebo in a ratio of 3:1 (active: 6, placebo: 2) and administered 0.05 mg/kg (Cohort 1), 0.1 mg/kg (Cohort 2), 0.5 mg/kg (Cohort 3), 1.0 mg/kg (Cohort 4) and 1.5 mg/kg (Cohort 5) of HM15912 or matching placebo. Healthy volunteers exposed to single ascending doses of HM15912 confirmed a favorable safety profile. Overall, 25 of 40 subjects reported at least one treatment emergent adverse event (TEAE) but all of the TEAEs were mild and moderate in severity. There have been no serious adverse events (SAEs) and no subjects have discontinued study due to adverse events (AEs). Plasma citrulline level, which is a biomarker for intestinal enterocyte mass, was measured to assess the PD property. The fasting plasma citrulline levels (nmol/mL) gradually increased by HM15912 administration from dose 0.5 mg/kg, and the values between 0.5 mg/kg and 1.5 mg/kg tended to be overlapped and saturated. Serum concentration of HM15912 reached its peak levels (mean t_{max}) in 71.8 to 142.9 hours. Mean terminal elimination $t_{1/2}$ of HM15912 was estimated to approximately 108 to 167.4 hours that could support a potential for once every 4-week dosing frequency. Based on these results, the Sponsor aims to develop HM15912 as a long-acting treatment option for subjects with SBS and Phase 2 trial for SBS patients is currently ongoing (NCT04775706, EudraCT: 2021-000176-11).

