7.3. Study Subject Replacement

- For both Parts 1 and 2, subjects who withdraw from the study for non-safety related reasons and who are considered to be non-evaluable with respect to the primary objective may be replaced at the discretion of the sponsor but the maximum number of meaningfully evaluable patients will be not more than planned 8.

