6.1.2 Intercurrent Event and Handling Strategies

Table 4 Handling of Intercurrent Events for the Primary Estimand

| Intercurrent event | Data collection and analysis |
|---------------------------------|---|
| Use of prohibited medication | Depending on the assessment of the type of prohibited medication in the determination of PK Population, data collected after the intercurrent event will be used in analysis in line with a treatment policy strategy or a while on-treatment policy. |
| Early withdrawal from the study | Depending on the assessment of the timing of early withdrawal from the study in the determination of PK Population, the intercurrent event will be handled via a while on-treatment policy. |

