6.1.3 Variable and Population-level Summary

To evaluate the effect of severe renal impairment on the pharmacokinetics of HM15912

following single SC dose, PK parameters will be summarized by endpoint as presented in Table 5.

Table 5 Population level summary for Primary endpoints

| Primary endpoint | Population-level summary |
|--|--|
| Maximum serum concentration (C_{max}) | |
| Area under the concentration-time curve from extrapolated to infinity ($AUC_{0-\infty}$) | Geometric mean ratio (GMR) and corresponding 90% confidence interval (90% CI) between each renal impairment cohort and normal renal function cohort (i.e. Cohort 2, Cohort 3, Cohort 4 versus Cohort 1, respectively) will be presented with descriptive statistics [number of subjects, arithmetic mean, SD, coefficient of variation (CV%), geometric mean, geometric mean CV% median, minimum, and maximum values]. |

To explore the robustness of inferences from the main estimator, a sensitivity analysis will be conducted targeting the same estimand. If the adjusted regression coefficient (R^2) is less than 0.8 or the extrapolated area under the curve ($AUC_{\%Extrap}$) exceeds 20%, those will be excluded from the sensitivity analysis.

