9.2.6 Pharmacokinetic Parameters

PK parameter will be presented for the PK population, and all available individual data will be listed for the Safety population.

PK parameters will be calculated using the standard NCA method with the log-up linear-down method of AUC. Actual sampling times will be used for deriving PK parameters.

The following PK parameters of HM15912 will be summarized.

Table 8 PK parameters

| Parameter | Description |
|-----------------------------|--|
| Primary endpoint | |
| $AUC_{0-\infty}^*$ | Area under the serum concentration-time profile (AUC) from time zero extrapolated to infinite time |
| C_{max} | Maximum serum concentration |
| Exploratory endpoint | |
| t_{max} | Time to maximum serum concentration |
| $t_{1/2}^*$ | Elimination half-life |
| Vd/F^* | Volume of distribution |
| CL/F^* | Clearance ($CL/F = Dose / AUC_{0-\infty}$) |
| λ_z^* | First order rate constant associated with the terminal (log-linear) portion of the curve |
| AUC_{last} | AUC from time zero to the last observable concentration |
| $AUC_{\%Extrap}^*$ | Percentage of $AUC_{0-\infty}$ due to extrapolation from t_{last} to infinity |

* As data permit

To determine the apparent first-order terminal elimination constant (λ_z), linear regression will be conducted by the logarithmically scaled concentration against time. The constant λ_z and its related parameters will be flagged and excluded in the statistical analysis if data points are

less than 3 after C_{max} .

In order to comparing the exposures among cohorts, box and whisker plots of C_{max} , $AUC_{0-\infty}$ and AUC_{last} will be generated.

After Part 1, PK parameter of HM15912 from severe renal impairment group (Cohort 2) will be estimated and compared to control group (Cohort 1). A one-way analysis of variance (ANOVA) will be used to compare log transformed PK parameter. The estimates of mean difference (Cohort 2 – Cohort 1) and corresponding 90% confidence intervals (CI), as well as each exponentiation of estimates will be presented to provide the estimates of geometric mean ratio. After statistical or clinical evaluation of results from Part 1, whether to proceed to Part 2 will be further discussed.

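### Does the SAP need a numeric rule to keep profiles that end before the expected peak out of the primary Cmax analysis?

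*SAP*

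**What the plan says.** **Who enters.** SAP section 5 (Table 3) defines the PK Population as "All subjects who have at least one evaluable HM15912 serum concentration after receiving any amount of HM15912", without important protocol deviations or events that significantly affect PK. Protocol 9.3 has the same definition. Neither document defines an evaluable concentration. Cmax and AUC0-∞ are both primary and both use this population.

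**How exclusions are decided.** SAP section 5 says that the classification will settle which subjects or data are left out of which analyses: "The decisions will be made before the database lock and will be documented and approved". For early withdrawal, SAP 6.1.2 (Table 4) begins "Depending on the assessment of the timing of early withdrawal from the study in the determination of PK Population" and then applies a while-on-treatment strategy. It gives no time or sample cut-off. SAP 9.1.2 provides for a review of all deviations before lock, and SAP 9.1.1 tabulates the reasons for exclusion.

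**Numeric profile rules.** There are two. In SAP 9.2.6, the terminal rate constant and its related parameters "will be flagged and excluded in the statistical analysis if data points are" fewer than three after Cmax. In SAP 6.1.3, profiles with adjusted R² below 0.8, or whose extrapolated area "exceeds 20%, those will be excluded from the sensitivity analysis". Neither acts on Cmax from a short profile.

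**Timing and replacement.** Protocol 2.2 reports mean tmax "in 71.8 to 142.9 hours". SAP 3.3 says that after Cohorts 1 and 2 complete, "preliminary analysis will be conducted to decide whether to proceed to Part 2, or not". Protocol 7.3 says that subjects who withdraw for non-safety reasons and "who are considered to be non-evaluable with respect to the primary objective may be replaced at the discretion of the sponsor".

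**The concern.** Cmax is the largest observed concentration, so it can be read from any profile, including one that stops while concentrations are still rising. On the population wording alone, a subject who leaves after the 24 h sample is in the PK Population, and that single value enters the ANOVA. AUC0-∞ is protected by the terminal-phase rule; Cmax is not.

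With 8 subjects per cohort, one low value matters. In Cohort 2 it pulls the Cmax ratio down and could hide raised exposure. In Cohort 1 it pushes the ratio up. The study is open-label, so cohort is known when membership is decided. No text says that Part 1 membership is fixed before the preliminary ratio is computed, and non-evaluable in the replacement rule is undefined.

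The natural remedy is a rule that Cmax counts only if a lower quantifiable concentration follows the observed maximum, with the same definition used for replacement.

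**Working it through.** **1. The plan's own precision figure.** Inputs from SAP section 4: 8 per cohort, between-subject SD 0.257 for ln AUC0-∞, two-sided 90% interval.

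Half width = t(0.95, 14) × SD × √(2/8) = 1.7613 × 0.257 × 0.5 = 0.2263. The SAP states 0.2260, which corresponds to an unrounded SD of about 0.2566. The figure reproduces.

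**2. How low a truncated Cmax would be.** Assumption: one-compartment model with first-order absorption. Inputs: tmax of 71.8, 100 and 142.9 h crossed with half-life of 108, 130 and 167.4 h (ends of the ranges in Protocol 2.2 plus an assumed middle value for each), giving nine pairs. Elimination rate ke = ln 2 / t½; the absorption rate ka is solved from tmax = ln(ka/ke)/(ka − ke). Let f be the highest concentration sampled up to the cut-off, divided by the highest on the full schedule in SAP Table 2.

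**3. Effect of one such subject in 8.** The cohort geometric mean is multiplied by f^(1/8). If the value is kept, that cohort's SD is taken as √(0.257² + (ln f)²/8), and the half width uses separate cohort variances, as in the SAP section 11 code. The AUC SD is assumed to hold for Cmax.

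If the subject is excluded (7 vs 8), half width = t(0.95, 13) × 0.257 × √(1/7 + 1/8) = 1.7709 × 0.257 × 0.5175 = 0.2356.

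| Last sample | f | Cohort mean multiplied by | Half width, kept | Half width, excluded | Pairs where keeping is better |
|---|---|---|---|---|---|
| 24 h | 0.386–0.698 | 0.888–0.956 | 0.240–0.313 | 0.236 | 0 of 9 |
| 48 h | 0.653–0.947 | 0.948–0.993 | 0.227–0.245 | 0.236 | 6 of 9 |
| 72 h | 0.828–1.00 | 0.977–1.00 | 0.226–0.230 | 0.236 | 9 of 9 |
| 96 h | 0.933–1.00 | 0.991–1.00 | 0.226–0.227 | 0.236 | 9 of 9 |

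Better means both a narrower interval and a smaller mean squared error of the cohort log mean: (ln f / 8)² + 0.257²/8 if kept, against 0.257²/7 if excluded. The two are equal at f = exp(−8 × 0.257 × √(1/7 − 1/8)) = 0.76. On interval width the break-even is about 0.74.

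**4. Size against the planned precision.** The worst 24 h case shifts the log ratio by |ln 0.386|/8 = 0.119, about half of 0.226. The worst 72 h case shifts it by |ln 0.828|/8 = 0.024, about a tenth.

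**5. What the proposed rule would do.** It removes every profile whose maximum is its last sample, so it also acts at 72 h and 96 h, where exclusion costs more than it gains. Among profiles ending at the same time, it keeps early peakers and drops late peakers. If tmax depends on renal function, exclusion would then differ by cohort. A chance high 24 h value followed by one lower value would still pass.

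**6. Replacement.** Protocol 7.3 refers to the primary objective, which covers Cmax and AUC0-∞. A Cmax-only definition would call a subject with one or two post-peak points evaluable, although SAP 9.2.6 removes that subject's terminal-phase parameters. This would weaken the endpoint that decides Part 2.

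**The case for a change.** The best case for a change is that a documented review is a procedure and not a criterion. The deviation clause is a weak route for withdrawals: stopping observation does not alter the drug's PK, and Protocol 7.2 says that missed early-discontinuation procedures are not deviations. Discharge is allowed after Day 2, so the 24 h cut-off coincides with a real decision point. If Part 2 runs, the final analysis comes long after the Part 1 ratio is known.

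Much of this stands as description: the SAP gives no criterion, and a 24 h value should not be kept. It does not show that the plan would keep one. SAP Table 4 directs attention to withdrawal timing when membership is set, and against a mean tmax of 71.8 h or later the answer for a 24 h profile is plain. Samples missed without withdrawal fall under the deviation and event clause and the review of subjects and data in SAP section 5. Individual profiles are plotted and listed (SAP 9.2.5), so a retained short profile would be visible.

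The 24 h case is also remote. Confinement runs by default to Day 8 (168 h), past the latest mean tmax. Early discharge needs the subject's request and the investigator's agreement, and Day 3 to 7 sampling continues after it. Protocol 7.2 expects withdrawal to be uncommon. The documents do not say who will see assay results when membership is decided, so bias from that source is possible but not shown. Computing the preliminary ratio already requires choosing the Part 1 set, and any later exclusion would have to be documented, approved and tabulated with its reason.

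**Conclusion.** This is missing detail that the planned review can fill sensibly. A cut-off near 24 h is the case with a consistent material effect: a factor of 0.89 to 0.96 on one cohort's geometric mean Cmax for one subject in 8, with exclusion better in all nine scenarios. At 48 h the better choice depends on the subject's peak time, and from 72 h keeping the value is better throughout. Judging by timing, as the SAP does, suits that pattern better than one fixed rule, and the specific rule considered here would do net harm for most cut-offs.

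The Part 2 decision rests on AUC0-∞, and a profile with no terminal phase gives no usable AUC0-∞, so the decision is untouched.

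The figures assume a one-compartment shape, the stated pairings of tmax and half-life, the AUC SD for Cmax, one truncated subject, and withdrawal unrelated to exposure. The tmax values are a range of means across the earlier study, not individual values. The documents give no dropout rate, so the chance of the 24 h case cannot be calculated.
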